4.4.2 Data Collection and Follow-up for Withdrawn Subjects

An attempt will be made to collect follow-up data for withdrawn subjects, as well as patients who undergo esophageal surgery (i.e., surgical histology of the resection site). These patients will be called to collect this data.

5 Study Device

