1.6 Anticipated Duration of the Clinical Investigation

Screening and enrollment will be performed at the time of consent for their endoscopy and anticipated resection. In eligible patients randomized to ECM placement, the endoscopy will require an additional 5-10 minutes for application of ECM. Follow-up will occur per standard of care in all patients undergoing EMR, that is endoscopy in 8-12 weeks or sooner for patient symptoms (e.g., dysphagia).

2 Study Objectives

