3.1 General Design

This is a randomized study on the efficacy of ECM in promoting constructive healing following endoscopic resection (EMR). 20 patients anticipated to undergo endoscopic resection will be recruited in the outpatient setting from the Barrett's Esophagus Unit. Prior to endoscopy, patients will complete a standardized questionnaire (Mayo Dysphagia Questionnaire) and the physician will use the Mellow-Pinkas scale to assess baseline dysphagia. Patients with lesions that lift and are amenable to cap-assisted EMR will be randomized to receive ECM to the defect site vs. standard of care. All patients should be on standard of care double dose proton-pump inhibitor therapy (Omeprazole 40mg PO daily or the equivalent); if this has not been initiated they will be provided a prescription .

In both groups, patients will be brought back for repeat standard of care clinic and endoscopic assessments in 12-16 weeks, or sooner if needed. A clinical dysphagia assessment will be performed with repeat of the above questionnaires. Endoscopy will involve inspection of the wound site, and images in white-light and electron chromoendoscopy will be taken for blinded evaluation later. Submucosal saline injection at the wound site will be performed to determine its ability to lift.

Any patients receiving esophageal dilations will be noted. Patients requiring esophagectomy will be excluded from the primary objective of the study but their surgical specimen at the site of endoscopic resection will be evaluated for evidence of constructive healing.

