4.4 Early Withdrawal of Subjects

4.4.1 When and How to Withdraw Subjects

Subjects will be withdrawn from the study if any adverse events related to EMR, or application of ECM occurs, including major bleeding, perforation, or infection. Patients will also be withdrawn if after EMR the patient proceeds to esophagectomy.

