7.1 Sample Size Determination

A power analysis was performed for this two independent sample study with a dichotomous endpoint (presence of a saline lift during follow-up EGD). We assume 20% of patients receiving standard of care and no ECM will have a submucosal lift vs. 80% of patients receiving ECM will have submucosal lift. Using a power of 0.8, and alpha of 0.05, this equates to a sample size of 10 for each group for a total of 20 subjects.

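### The only collection method named for withdrawn subjects is a call, which cannot give a lift grade, and the plan does not say that lift is graded when subjects withdrawn for an adverse event return for endoscopy

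*Combined protocol and SAP*

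**What the plan says.** Section 4.4.1 sets two triggers for withdrawal. The first is an adverse event: "Subjects will be withdrawn from the study if any adverse events related to EMR, or application of ECM occurs". The second is esophagectomy after EMR.

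Section 4.4.2 covers data after withdrawal. It promises an attempt to obtain follow-up data, and surgical histology for operated patients, and then says: "These patients will be called to collect this data". It names no other method and does not list the lift grade among the items to collect.

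The primary outcome is measured at Visit 3 (6.3). Saline is injected at the healed site and the endoscopist records no, partial or complete lift.

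Routine endoscopy is planned for everyone. Section 1.6 states: "Follow-up will occur per standard of care in all patients undergoing EMR, that is endoscopy in 8-12 weeks". Sections 3.1 and 6.3 also bring patients back, at 12-16 weeks, and neither exempts withdrawn subjects.

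For patients who go on to esophagectomy, section 3.1 says that "their surgical specimen at the site of endoscopic resection will be evaluated for evidence of constructive healing".

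On analysis, section 5.4 excludes patients lost to follow-up or referred for surgery from the primary objective, and does not mention adverse-event withdrawals. Section 7.3 limits the population to completers but allows this to be relaxed. Section 7.2 expects no missing data.

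**The concern.** Section 4.4.2 is the one provision written for withdrawn subjects, and the method it names cannot produce the primary endpoint. A site that follows it for a subject marked as withdrawn could reasonably telephone, record what the patient reports, and not grade lift when that patient comes back for routine endoscopy.

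The loss would not be random. Withdrawal follows events in the resection or in applying the matrix, and these may be related to healing. Events of matrix application can occur only in the ECM arm, so the loss can also differ by arm. That can bias the comparison as well as reduce its precision.

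This is a question of collection and comes before the choice of analysis set. Widening the set later cannot supply a grade that was not recorded at the time. Only imputation or exclusion would then remain.

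**Working it through.** **Inputs.** All are from section 7.1.
- Control rate: "We assume 20% of patients receiving standard of care and no ECM will have a submucosal lift", so p1 = 0.20.
- ECM rate: "80% of patients receiving ECM will have submucosal lift", so p2 = 0.80, a difference of 0.60.
- Error rates: "Using a power of 0.8, and alpha of 0.05". Sidedness is not stated; two-sided is assumed.
- Size: "a sample size of 10 for each group for a total of 20 subjects". No allowance for withdrawal is made.

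**Step 1: reproduce the plan's sample size.** Use the normal approximation with pooled variance under the null and no continuity correction. The mean rate is 0.50.

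n per arm = [1.960 × √(2 × 0.5 × 0.5) + 0.842 × √(0.16 + 0.16)]² / 0.60² = (1.386 + 0.476)² / 0.36 = 9.6, rounded up to 10.

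This matches the plan.

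**Step 2: power with complete and incomplete grading.** Power = Φ[(0.60 − 1.960 × SE0) / SE1]. SE0 uses the pooled rate and SE1 the separate rates.
- 10 vs 10: SE0 = √(0.25 × 0.2) = 0.2236 and SE1 = √(0.16 × 0.2) = 0.1789. Then Φ(0.904) = 81.7%.
- 10 vs 9: the pooled rate is 9.2/19 = 0.484, SE0 = 0.2296 and SE1 = 0.1838. Then Φ(0.816) = 79.3%.

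The losses below are assumed. Exact power is by full enumeration of the two-sided Fisher test.

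| Graded per arm | Normal approximation | Fisher exact |
|---|---|---|
| 10 vs 10 | 81.7% | 63.5% |
| 10 vs 9 | 79.3% | 67.9% |
| 10 vs 8 | 76.4% | 63.2% |
| 9 vs 9 | 76.8% | 62.5% |
| 8 vs 8 | 70.9% | 59.8% |

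The exact figures do not fall steadily, because the test is discrete at these sizes. The statement that one lost outcome takes power below 80% therefore belongs to the approximation that reproduces the plan's sample size. It is not a general law.

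**Step 3: uncertainty left by an ungraded patient.** If one of 10 is ungraded and x of the other nine lift, the arm's rate lies between x/10 and (x + 1)/10, a width of 10 points. One ungraded patient in each arm leaves the difference uncertain by 10 + 10 = 20 points from worst to best case, against the assumed effect of 60 points.

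**Step 4: selective loss, with assumed counts.** Suppose 6/10 lift on ECM and 2/10 on control. The difference is 40 points and Fisher p = 0.170. If two non-lifting ECM patients are withdrawn and never graded, the data become 6/8 vs 2/10. The difference is then 75% − 20% = 55 points and p = 0.054. Two lost grades add 15 points to the apparent effect. This shows what could happen and is not a forecast.

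**The case against.** The strongest reply is that nothing in the plan rules out grading. Section 4.4.2 does not make the call exclusive and does not say that withdrawn subjects miss Visit 3. Sections 3.1 and 6.3 bring patients back with no exception. This stands. A reader might infer that the lift grade is never collected after withdrawal, and the documents do not support that. What they show is silence on a point that should be explicit.

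A reader might also infer that surgical histology is lost because it hangs on a call. That does not hold either. Section 3.1 already plans evaluation of the specimen, and a call may serve to locate the surgical record. Lift is normally unobtainable after esophagectomy, and 3.1 and 5.4 already take those patients out of the primary objective. The point is therefore confined to adverse-event withdrawals.

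A third reply is that a completers-only population makes extra grades worthless. This is only partly right. Section 5.4 does not exclude adverse-event withdrawals, and under 7.3 a subject graded at Visit 3 could count as a completer, so collection can change the result. The plan should still say so.

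Two cautions also stand. First, the arithmetic assumes that 10 per arm are enrolled, whereas section 8.5 halts enrolment after an adverse event in any subject. Second, the examples in 4.4.1 include major bleeding, perforation and infection, so whether to inject the site after such an event is a clinical decision that the statistical fix must not prescribe.

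**Conclusion.** The concern holds as a gap in the provision for collecting data. The plan withdraws subjects after events that can differ by arm, names for them only a method that cannot yield the lift grade, and does not say that lift is graded at the endoscopy they are due to attend.

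Each ungraded patient costs 10 points of certainty in that arm's rate. By the normal approximation, one lost outcome brings power from 81.7% to 79.3%, just below the planned 80%. The possible bias matters more than this small loss of power.

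The size rests on full enrolment of 10 per arm, the rates in section 7.1, a two-sided test, and an assumed number of withdrawals. One to three of 20 (5% to 15%) is a working range; the documents give no rate. The gap should be closed because the grade cannot be recovered after Visit 3 and the remedy is cheap.

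**What to change.** Amend 4.4.2 to say that subjects withdrawn for an adverse event who still consent remain in data collection. At the follow-up endoscopy they already attend, the Visit 3 lift grade, images, dysphagia questionnaire and any dilations are recorded. Whether the saline injection is performed is left to the treating endoscopist; if it is not, the reason is recorded.

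State that graded subjects enter the primary analysis in the arm to which they were randomized, and reconcile 4.4.1, 4.4.2, 5.4, 6.3 and 7.3 accordingly. The timing of the follow-up endoscopy also needs reconciling: 1.6 gives 8-12 weeks, and 3.1, 5.4 and 6.3 give 12-16.

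For operated subjects, only align 4.4.2 with the specimen evaluation already planned in 3.1.

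The cost is a few sentences and no additional endoscopy. The small downside is a few minutes for the lift test in a few subjects, and consent wording that separates withdrawal from refusal of further data collection.

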5.1 Description

ECM products such as those produced by Acell are approved by the FDA to aid in the healing of wound sites like those created by EMR. The product that will be used in this study is the A-cell Matristem, which is derived from porcine bladder (also known as urinary bladder matrix). Observations pertaining to this specific product have been reported in several clinical series, including use in patients undergoing esophageal surgery and hiatal hernia repair.¹⁸⁻²⁰

[figure not shown]
The device is supplied in sheets of varying sizes and thickness. Only one thickness will be used for all patients, whereas the smallest sized sheet that adequately covers the defect site will be selected and applied by the endoscopist. Identifying product information including serial, lot, and/or batch numbers will be recorded for each patient.

5.2 Method for Assigning Subjects to Treatment Groups

Patients will be randomized using prepackaged envelopes to ECM or standard of care and stratified based on the size and number of EMR performed during the procedure. Thus, randomization will occur during the procedure immediately following resection.

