1.4 Clinical Data to Date

Observations on the use of ECM in the human esophagus have been reported in several series. Scaffolds from porcine urinary bladder were used to treat five BE patients with high-grade dysplasia/ esophageal adenocarcinoma and long-segment BE (8 to 13cm) following ESD.⁸ The scaffold was applied using a temporary stent that was removed within 9-17 days, allowing scaffold integration with the underlying muscular wall of the esophagus. Complete epithelialization and formation of a new submucosal layer was appreciated during follow-up. All patients required transient postoperative dilation for mild stricture formation in areas not covered by ECM, but were able to then tolerate a normal diet without recurrence of disease during 4-24 month follow-up. No other significant complications were reported. ECM scaffold degradation was noted to occur *in vivo* rapidly without any evidence of residual xenogeneic tissue. Using a similar approach, three additional patients were subjected to endoscopic, circumferential *en bloc* resection of Barrett's with HGD, followed by fundoplication.¹⁶ One patient with incomplete ECM coverage developed an easily dilated stricture, whereas the remaining 2 patients who had complete ECM coverage did not. To date, no randomized clinical trials exist comparing the use of ECM in humans following EMR vs. the current standard of care (i.e., observation).

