5.3 Preparation and Administration/Implantation of Investigational Device

The smallest sized version of material that adequately covers the defect site will be selected for application. Application will involve attachment of the corners of the material to healthy tissue surrounding the defect site using four standard endoscopic clips as depicted below. These clips are designed to slough following healing and rarely cause nuisance or complications to patients. X-tac is also a similar method but using screws instead.

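### Coverability of the defect is not confirmed before the envelope is opened, so any defect a sheet cannot cover would affect the ECM arm alone and could dilute or bias the lift comparison

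*Combined protocol and SAP*

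**What the plan says.** Allocation is by envelope, "stratified based on the size and number of EMR performed during the procedure", and section 5.2 adds: "Thus, randomization will occur during the procedure immediately following resection".

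The procedural condition for randomization describes the lesion before it is removed. Section 3.1 reads: "Patients with lesions that lift and are amenable to cap-assisted EMR will be randomized"; section 6.2 likewise asks only that the patient be suitable for standard EMR. The criteria in 4.1 and 4.2 set no limit on the size or number of defects and no requirement that a sheet can cover them.

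Coverage appears only as a rule for choosing the sheet. Section 5.1 says that "the smallest sized sheet that adequately covers the defect site will be selected and applied by the endoscopist", and section 5.3 describes application as "attachment of the corners of the material to healthy tissue surrounding the defect site". The plan gives no largest sheet size, no definition of adequate coverage, and no rule for a defect that cannot be covered. Section 3.4 counts technical and device failures under safety. Section 7.3 analyses completers of all study procedures, and allows this to be relaxed to those who completed most of them.

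**The concern.** Only the ECM arm can fail on coverage. The same defect in a control patient has no consequence, because nothing is placed. A coverage problem found after the envelope is opened therefore acts on one arm, and it can no longer be handled symmetrically.

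The protocol's own background suggests that coverage matters. In the first esophageal series in section 1.4, "All patients required transient postoperative dilation for mild stricture formation in areas not covered by ECM". In the second, "One patient with incomplete ECM coverage developed an easily dilated stricture", while the two patients with complete coverage did not.

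With 10 patients per arm, one such patient is 10% of the ECM arm. A null result could then mean either that ECM does not help or that it did not cover the defect. A positive result could partly reflect the loss of harder defects from one arm.

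**Working it through.** **Inputs from the plan.** Section 7.1: lift in 20% of controls and 80% of ECM patients, power 0.8, alpha 0.05, 10 per arm. Section 7.2: unpaired t-test on lift. Sidedness is not stated; two-sided is assumed.

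**Not in the plan.** How many defects cannot be covered, how often they lift, and whether section 7.3 keeps such patients. Each is varied below as an assumption.

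**1. The plan's figure.** Two proportions, pooled variance, no continuity correction:

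n = [1.960 × √(2 × 0.5 × 0.5) + 0.842 × √(0.2 × 0.8 + 0.8 × 0.2)]² / 0.6² = (1.386 + 0.476)² / 0.36 = 9.63, so 10 per arm.

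This matches section 7.1. Enumerating every outcome at 10 + 10, the t-test has power 0.805.

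**2. Analysed as assigned, worst case.** Let m of the 10 ECM patients be uncovered and lift at the control rate. The expected ECM rate is [0.8 × (10 − m) + 0.2 × m] / 10 = 0.80 − 0.06m. Power is by exact enumeration.

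| Uncovered (m) | ECM lift | Difference from 20% | Power |
|---|---|---|---|
| 0 | 80% | 60 points | 0.805 |
| 1 | 74% | 54 points | 0.708 |
| 2 | 68% | 48 points | 0.588 |
| 3 | 62% | 42 points | 0.457 |

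**3. Averaged over an assumed frequency.** If a share q of defects cannot be covered and m is Binomial(10, q), average power is 0.754 at q = 5%, 0.699 at 10% and 0.582 at 20%. The chance of at least one such ECM patient is 1 − 0.95¹⁰ = 0.40 at 5% and 1 − 0.90¹⁰ = 0.65 at 10%.

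**4. Partial coverage.** If one incompletely covered patient lifts at, say, 50% (an assumption, midway between the two planned rates), the expected ECM rate is (9 × 0.8 + 0.5) / 10 = 77% rather than 74%. Half of the worst-case loss in the difference disappears.

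**5. Dropped by the completer rule.** There is then no dilution, but the matching control patients stay in. For illustration, suppose ECM has no effect, lift is 20% overall, and uncoverable defects never lift. Dropping a share u from the ECM arm raises its rate to 0.20 / (1 − u):

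- u = 10%: 22.2%, bias +2.2 points
- u = 20%: 25.0%, bias +5.0 points
- u = 30%: 28.6%, bias +8.6 points

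The bias favours ECM. The text does not settle whether step 2 or step 5 applies.

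**The case against.** The strongest reply is that such defects may be rare. Sheets come in varying sizes and are chosen to fit. Section 1.1 says most endoscopists limit EMR to defects of 2 cm or half the circumference, and section 1.5.1 leaves more extensive resections to later studies. This bears on frequency and stands as far as it goes. But the limit in 1.1 is background, not a criterion, and the sheet rule presumes a fit that nobody verifies before assignment.

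The evidence in 1.4 is also indirect. One could count strictures in 6 of 8 patients (5 of 5 and 1 of 3) linked to gaps in coverage. Those were longer or circumferential resections with the scaffold held by a temporary stent, and the outcome was stricture, not lift. Nothing says the gaps could not have been covered. The first series also reports a new submucosal layer despite them. So 6 of 8 is not a rate for this trial, and treating an uncovered patient as equal to a control is a worst case.

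Finally, in a feasibility trial it is defensible to randomize every EMR-amenable defect, and stratifying by size and number helps balance hard defects between the arms. Stratification does not stop the failure from acting on one arm. Counting coverable and uncoverable defects among all resected patients would still yield the feasibility information.

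**Conclusion.** The gap is real: assignment follows resection, but coverability is not confirmed first, and only the ECM arm can suffer from it. The effect could be dilution or a bias towards ECM, depending on how section 7.3 is applied.

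The power figures, from 0.805 down to 0.71, 0.59 or 0.46 with 1, 2 or 3 of 10 uncovered, rest on the plan's 80% and 20%, a two-sided t-test, analysis as assigned, and uncovered patients lifting at the control rate. They are worst cases for those counts, and the counts themselves are assumptions.

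A reader might infer that uncoverable defects will occur and will dilute the ECM arm, or that an uncovered ECM patient is simply untreated. The documents support neither: they give no frequency, the series in 1.4 does not show absence of benefit, and the completer set leaves the direction open. The point is a cheap improvement, not a demonstrated flaw in the result.

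**What to change.** In sections 5.2 and 6.2, add:

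> After resection and before the envelope is opened, the operator records for every resected patient whether an available sheet can adequately cover the defect when attached as in section 5.3. Only patients with a yes are randomized. The number with a no is reported. For ECM patients, coverage after placement is recorded as complete or incomplete.

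In section 7.3, add:

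> Every randomized patient with a lift result is included in the primary comparison in the assigned arm, including those whose patch was not placed or did not fully cover the defect.

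The investigators should state what they count as adequate coverage. Envelopes should be sealed and opaque, and the answer recorded before opening, so that the assignment cannot influence the judgement.

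**Cost.** Two CRF items, with no change in the timing of randomization. The result would apply to coverable defects only, and a few resected patients would not be randomized. The check does not prevent later detachment of the patch; the rule in 7.3 covers those patients. It also adds an operator judgement just before assignment, which is why concealment and the order of recording matter.

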5.3 Preparation and Administration/Implantation of Investigational Device

The smallest sized version of material that adequately covers the defect site will be selected for application. Application will involve attachment of the corners of the material to healthy tissue surrounding the defect site using four standard endoscopic clips as depicted below. These clips are designed to slough following healing and rarely cause nuisance or complications to patients. X-tac is also a similar method but using screws instead.

5.4 Subject Compliance Monitoring

Per endoscopic resection protocol, patients will be scheduled for follow-up in 12-16 weeks for repeat endoscopic assessment. Aside from continued use or initiation of proton pump inhibitor therapy (which will be assessed by patient history) there are no interim monitoring requirements for the patient. Patients lost to follow-up or referred for esophageal surgery will be excluded from analysis for the primary objective.

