5.8.4 Return or Destruction of Study Device

We will order clinical supply as needed and dispose of unused supply. We do not anticipate needing to return supplies.

6 Study Procedures

6.1 Visit 1

Patients will be recruited from the Barrett's Esophagus Clinic. Patients referred for endoscopic evaluation of Barrett's esophagus with high grade dysplasia, esophageal nodules or early esophageal cancer and are scheduled for EMR, will be screened using inclusion and exclusion criteria outlined above. Patients meeting inclusion criteria will be consented for study inclusion and will be asked to complete the Mayo Dysphagia Questionnaire.

6.2 Visit 2

Visit 2 refers to the procedure during which the patient will undergo planned EMR of the esophageal lesion. Visits 1&2 may take place on the same date. Patients will undergo endoscopy and those amenable to standard EMR will be randomized to receive ECM or receive standard of care (i.e., observation). ECM will be applied to patients in the manner described above.

6.3 Visit 3

All patients will be scheduled to return in approximately 12-16 weeks (up to 6 months) following EMR for follow-up endoscopic evaluation. Patients will repeat the Mayo Dysphagia Questionnaire prior to endoscopy. During endoscopy, the EMR site will be inspected and multiple pictures will be taken in white-light as well as electron chromoendoscopy (i.e., narrow band imaging). Thereafter, standard submucosal saline injection of the healed EMR site will be performed, and the endoscopist will record whether no lift, a partial lift, or complete lift was observed. Symptomatic structuring will be treated with standard pneumatic dilation.

Schedule of Events			
Study Activity	Baseline*	Procedure*	Follow-up procedure (3-4 months)
Consent	X		
History	X		X
Physical Exam	X	X	X
Disease State Symptom Survey	X		X
Concurrent Medications	X	X	X
Adverse Events		X	X
Serious Adverse Events		X	X

*Baseline and Procedure may be on the same date/visit.

7 Statistical Plan

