Any adverse event that results in hospitalization or prolonged hospitalization should be documented and reported as an unanticipated adverse device effect unless specifically instructed otherwise in this protocol. Any condition responsible for surgery should be documented as an adverse event if the condition meets the criteria for an adverse event.

Neither the condition, hospitalization, prolonged hospitalization, nor surgery are reported as an adverse event in the following circumstances:

- Hospitalization or prolonged hospitalization for diagnostic or elective surgical procedures for a preexisting condition. Surgery should **not** be reported as an outcome of an adverse event if the purpose of the surgery was elective or diagnostic and the outcome was uneventful
- Hospitalization or prolonged hospitalization required to allow efficacy measurement for the study
- Hospitalization or prolonged hospitalization for therapy of the target disease of the study, unless it is a worsening or increase in frequency of hospital admissions as judged by the clinical investigator.

Post-study Adverse Event

All unresolved adverse events should be followed by the investigator until the events are resolved, the subject is lost to follow-up, or the adverse event is otherwise explained. At the last scheduled visit, the local investigator should instruct each subject to report, to the local investigator, any subsequent event(s) that the subject, or the subject's personal physician, believes might reasonably be related to participation in this study. The local investigator should notify the Mayo IRB of any death or adverse event occurring at any time after a subject has discontinued or terminated study participation that may reasonably be related to this study. The IRB should also be notified if the local investigator should become aware of the development of problems, cancer or of a congenital anomaly in a subsequently conceived offspring of a subject that has participated in this study.

Preexisting Condition

A preexisting condition is one that is present at the start of the study. A preexisting condition should be recorded as an adverse event if the frequency, intensity, or the character of the condition worsens during the study period.

Unanticipated Problems Involving Risk to Subjects or Others (UPIRTSO)

Any unanticipated problem or adverse event that meets all of the following three criteria:

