8.5 Stopping Rules

Should an adverse event occur in any subject, further enrollment would be stopped immediately.

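### No safety contact is scheduled between the procedure and Visit 3, so the immediate enrollment stop depends on events seen at the procedure or volunteered by patients

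*Combined protocol and SAP*

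**What the plan says.** - **Schedule of Events (section 6).** There are three columns: baseline, procedure, and follow-up at 3-4 months. The AE and SAE rows are marked at the procedure and at follow-up only.
- **Section 5.4.** "patients will be scheduled for follow-up in 12-16 weeks for repeat endoscopic assessment". Apart from acid-suppressant use, "there are no interim monitoring requirements for the patient".
- **Section 6.3.** "All patients will be scheduled to return in approximately 12-16 weeks (up to 6 months) following EMR for follow-up endoscopic evaluation".
- **Section 3.1.** Return is "in 12-16 weeks, or sooner if needed". Section 1.6 also allows an earlier return for symptoms, but puts routine follow-up at 8-12 weeks, as does section 1.5.2.
- **Section 8.2.** Events are sought at each contact and at study visits.
- **Section 8.1.** The AE reporting period is 90 days after study treatment. Under the post-study heading: "At the last scheduled visit, the local investigator should instruct each subject to report" later events that might be related to the study.
- **Section 4.4.2.** Telephone calls are planned only for subjects who have been withdrawn or have gone to surgery.
- **Section 8.5.** "Should an adverse event occur in any subject, further enrollment would be stopped immediately".
- **Section 4.4.1.** Subjects are withdrawn for events related to the resection or the matrix, "including major bleeding, perforation, or infection".
- **Sections 8.3 and 8.3.2.** Unanticipated device effects are reported to the IRB within 5 working days and to the FDA within 10, counted from the investigator's notice.

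**The concern.** Three safety mechanisms act on the investigator's knowledge of an event: the enrollment stop, the withdrawal rule and the reporting clocks. The plan gives no routine way to obtain that knowledge during the weeks after discharge. If a patient has a bleed or infection at home and does not tell this unit, it may first be learned by recall at Visit 3. Until then enrollment continues, and about half of the new subjects receive the matrix.

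There is also a measurement cost. SAE incidence is a primary safety endpoint (3.4). Recall after three months or more tends to lose milder events and blur the dates of the rest, in both arms.

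**Working it through.** The plan gives no figure for this delay, so there is none to reproduce.

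**1. Is there a contact in the gap?** The Schedule of Events has no column between the procedure and follow-up. Section 8.2 adds questioning at contacts but creates none. The calls in 4.4.2 reach only subjects already known to have been withdrawn or sent to surgery. The regular SAE assessment in 8.6 states no frequency and no means of obtaining data. The gap is real, and the Schedule shows it without relying on 5.4.

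**2. AE period against the visit window.** 90 / 7 = 12.9 weeks. Of the 4-week window from week 12 to week 16, 16 - 12.9 = 3.1 weeks fall after the period ends, as does everything from there to 6 months. So the one routine post-procedure questioning usually comes after the period has closed. A visit at 8-12 weeks (1.5.2, 1.6) would fall inside it, which is one more reason to reconcile the intervals.

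**3. Subjects enrolled during the delay.** Inputs: 20 subjects (3.1, 7.1) and a 1-year overall duration (Study Summary). Assumptions: even accrual, the year includes the last subject's follow-up, and the event occurs soon after the procedure.

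Further subjects = 20 / (52 - v) × v, where v is the week of Visit 3.

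| Visit 3 | Accrual | Further subjects |
|---|---|---|
| 8 weeks | 44 weeks | 20/44 × 8 = 3.6 |
| 12 weeks | 40 weeks | 20/40 × 12 = 6.0 |
| 16 weeks | 36 weeks | 20/36 × 16 = 8.9 |

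If the year is accrual only, 20/52 × 12 = 4.6 and 20/52 × 16 = 6.2. With 10 per group (7.1), about half would receive the matrix: 3.6/2 = 1.8 to 8.9/2 = 4.4.

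**4. Cap by the subjects left to enroll.** If the event is equally likely in each of the 20 subjects, the number who can follow subject k is at most 20 - k.
- A delay worth 6 subjects averages (14 × 6 + 15) / 20 = 5.0.
- A delay worth 9 averages (11 × 9 + 36) / 20 = 6.8.

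The figures in step 3 are therefore upper figures, for an event early in accrual.

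**5. What a contact would change (illustrative times only).**
- At 1 week: 20/52 × 1 = 0.4 to 20/36 × 1 = 0.6 further subjects.
- At 4 weeks: 20/52 × 4 = 1.5 to 20/36 × 4 = 2.2.

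**The case against.** The best defense is that standard-of-care follow-up is a deliberate choice in a 20-subject feasibility study, and that the plan is not blind in the gap. Events at the procedure are recorded that day. Patients may return early for symptoms (1.6, 3.1), and 8.2 applies to those unscheduled contacts. The sentence in 5.4 belongs to a compliance section. All of this is correct, and it limits the point to post-discharge events that the patient does not bring to this unit. It does not close the gap, because the early-return route is unscheduled and starts with the patient.

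A reader might infer four stronger things that the documents do not support:
- **That the stop cannot act in time.** It can, for events seen at the procedure or reported early. Treatment at another hospital is a plausible scenario, but the documents give no rate for it.
- **That the stop is the only safeguard.** Section 7.2 says SAEs prompt immediate re-evaluation of study methods, and 8.6 requires regular SAE assessment and a site safety-monitoring plan. Neither states how events before Visit 3 would become known.
- **That patients are told to report events only at the last visit.** The consent pages are not available, and they may tell patients to call. The 8.1 sentence is a post-study instruction and is silent on earlier events.
- **That all 19 other subjects could be enrolled first.** This needs the event in the first subject, a visit at the 6-month limit, and accrual compressed to 52 - 26 = 26 weeks. With that visit delay but longer accrual, the figure is 20/52 × 26 = 10 to 20/36 × 26 = 14, before any cap.

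One objection to the remedy also stands. Section 8.5 has no seriousness threshold and no limit by arm, so calls that elicit minor complaints could, read literally, halt enrollment.

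**Conclusion.** The point holds in this form: no safety contact is scheduled between the procedure and Visit 3, and prompt operation of 8.5, 4.4.1 and the reporting clocks depends on events seen at the procedure or volunteered by patients. The gap itself is certain from the Schedule of Events.

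Its size is less certain. Roughly 4 to 9 further subjects could be enrolled before an unreported early event is discovered. This assumes even accrual, follow-up inside the 1-year duration, and visits at 8 to 16 weeks. It is conditional on an event whose probability the documents do not give, and it falls when averaged over which subject has the event. Even the lower figure is material among 20 subjects. This is a cheap improvement that should be made; it does not invalidate the design.

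**What to change.** 1. Add one or two scripted AE telephone contacts to the Schedule of Events, identical in both arms and at early times set by the investigator. They should ask about symptoms and any care received elsewhere. Amend 5.4 to match.
2. At discharge from Visit 2, instruct subjects to report any event or outside care. Keep the post-study instruction in 8.1 as it is.
3. Reconcile the 90-day AE period with the Visit 3 window, together with the differing follow-up intervals (8-12 weeks in 1.5.2 and 1.6; 12-16 weeks in 3.1 and 5.4; up to 6 months in 6.3).
4. Reconcile the trigger in 8.5, any adverse event, with 7.2, which refers to serious ones. Do this before the calls begin, so that minor complaints do not have an unintended effect. The choice of trigger is for the investigator and the IRB.

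**Cost.** A protocol amendment and at most 20 × 2 = 40 short calls, with no new visit or procedure. More minor events will be recorded. If 8.5 stays as literally worded, a call could halt enrollment.
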